Visual Analog Scales (VAS) for Patient Assessment. Additionally, it is necessary to consider other approaches to assess fluid status that are more clinically oriented. There continues to be substantial controversy surrounding the accuracy of a number of clinical assessments to document improvement in worsening heart failure. Both the nature of the

symptom and sign assessment as well as the type of measurement used remains in dispute. However, scales that measure symptomatic dyspnea remain a major tool to quantify the effect of treatment strategies to reverse worsening heart failure. Documenting improvement in patient reported dyspnea by the 10-point VAS is generally well accepted as evidence of clinical effectiveness of an intervention. This scale has been used in a number of acute heart failure trials. Therefore changes in the VAS dyspnea scale from baseline to Visit 2 is designated as the highest priority secondary endpoint in this trial. It is important to note that due to measurement variability, VAS and Likert scales are relatively insensitive ways to determine changes in patient symptoms and substantial sample sizes are needed to have power to detect significant differences especially between placebo and drug groups. The present study sample size is not adequate for this purpose. However, observed changes may be compared to those seen in larger acute heart failure trials to give hypothesis generating signals of tolvaptan efficacy.

Changes in Loop Diuretic to Reflect Clinical Status. Recent work with tolvaptan has documented that background loop diuretic therapy does not remain the same in tolvaptan and placebo groups throughout the study period. Although well recognized to be a confounder of the interpretation of the efficacy of tolvaptan therapy in addition to loop diuretics, studies to date have not been well designed to capture detailed information on changes in loop and other diuretics during the study period. In contrast, the present study is designed to collect detailed information on type of diuretic as well as dose in conjunction with extensive clinical assessments at specific visits during the study. This will assist in correlation of clinical findings with changes in diuretic dosing in the study arms.

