6.2.2 Baseline Assessments

At the time of randomization, all study subjects will undergo:

- History and physical examination focused on signs and symptoms of congestion
- Assessment of the degree of congestion and dyspnea present
- Vital signs (including blood pressure and body weight)
- Documentation of current cardiovascular medications
- Measurement of Creatinine, BUN, electrolytes, and serum osmolarity
- Serum pregnancy test for women of child bearing potential

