7.1 Primary Endpoint

The primary endpoint for the study will be change in body weight between patients randomized to tolvaptan versus placebo from baseline to 48 hours with and without stratification for baseline copeptin level.

7.2 Secondary Endpoints – Congestion Indices and Body Weight.

7.2.1 Change in the patient reported visual analog scale for dyspnea from baseline to 48 hours.

7.2.2 Change in loop diuretic dose (mg furosemide) at 48 hours.

7.2.3 Loop Diuretic Adjustment defined as decrease versus no change or increase in loop diuretic dosing at 48 hours.

7.2.4 Change in Loop Diuretic Score defined based on change in loop diuretic dosing.

7.2.5 Change in body weight from baseline to 8 days.

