8.3.1 VAS Score. The highest priority secondary endpoint will be based on the patient reported VAS dyspnea score with comparison of the change in this scale from Visit 1 to Visit 2 by treatment group. Based on previous experience with this scale, the current study will not have statistical power to determine if there is a difference between the tolvaptan and placebo group in VAS dyspnea results. However, this dyspnea score has been widely used in previous trials of acute heart failure and may provide a signal of potential benefit of tolvaptan.

8.3.2 Change in Loop Diuretic Dose at Visit 2. The next highest priority secondary endpoint will be based on changes in loop diuretic dosing in the study patients at Visit 2. Doses of loop diuretic will be converted as necessary to milligram (mg) equivalents of furosemide dose by the following definitions: 1 mg of bumetanide = 40 mg of furosemide and 1 mg of torsemide = 20 mg of furosemide. The difference of interest will be the dose of loop diuretic at the end of Visit 2 minus the dose at the start of Visit 2 (expressed as mg equivalents of furosemide).

8.3.3 Categorical Assessment of Loop Diuretic Use at Visit 2 – Loop Diuretic Adjustment. Clinical experience strongly suggests that changes in dosing of loop diuretics during the trial would be a strong indicator of changes in congestion status. Specifically, a decision to increase loop diuretic dose during Visit 2 would equate to

worsening congestion while a decision to reduce loop dose during Visit 2 would reflect improvement in volume status and less congestion.

During the development of this aspect of the analysis plan (still in the blinded period of the study), the investigators assumed that the pattern of changes in loop dose use would be similar to that of patients with acute heart failure where increases in doses of loop diuretic are typical. Thus, the initial analysis for loop dose adjustment was based on increases in loop dose at Visit 2 or the addition of metolazone.

However, when blinded aggregate study results were reviewed, the opposite pattern was found. The aggregate blinded data revealed that loop doses on the whole decreased rather than increased at Visit 2 and no additional diuretics were added. These observations led to a final analytical approach, where dichotomous response was characterized as favorable when loop doses were decreased and unfavorable when loop doses stayed the same or were increased.

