8.5 Statistical Analysis of Study Results

8.5.1 General Statistics. Descriptive statistics will be generated for a comprehensive set of study variables to determine measures of central tendency and dispersion, as well as to characterize the nature of their distributions and whether outliers existed in the data. Continuous values will be reported as mean \pm standard deviation and categorical values as frequencies and percentages.

8.5.2 Analysis of the Primary Endpoint. The comparison of change in body weight from baseline to 48 hours between the two treatment groups constituted the primary endpoint. Hypothesis testing on this between-group change was performed by

nonparametric methods using the Wilcoxon rank-sum test via SAS PROC NPAR1WAY; a two-sided significance level of .05 was applied. This analysis of change in body weight was compared between all tolvaptan treated patients and all placebo treated patients on an intention-to-treat basis. Within-group changes over time were analyzed via the nonparametric Wilcoxon signed-rank test using SAS PROC UNIVARIATE under a two-sided significance level of .05. The second analysis of the primary study endpoint, comparison of change in body weight between treatment groups at 48 hours **with stratification** for baseline copeptin, will be conducted in the same manner as the priority comparison.

8.5.3 Analysis of Secondary Endpoints.

A two-sided significance level of .05 will also be applied to statistical testing of secondary endpoints with no adjustment for multiple comparisons.

8.5.3.1 Changes in VAS Scale. Changes in the VAS dyspnea scale will be analyzed via point estimates and corresponding standard deviations. Supportive between-treatment group comparisons will be conducted via the Wilcoxon rank-sum test.

8.5.3.2 Change in Loop Dose. For this continuous variable (dose of loop diuretic in furosemide mg equivalents) between-group comparisons will be assessed via t-test.

8.5.3.3 Loop Diuretic Adjustment. The Fisher's exact test will be used to assess between-group comparisons for this dichotomous variable.

8.5.3.4 Change in Loop Diuretic Score. For this ordinal variable between-group comparisons will be assessed via t-test.

8.5.3.5 Change in body weight from Visit 1 to Visit 3. This endpoint will be analyzed in a similar fashion as the change in body weight from Visit 1 to Visit 2.

8.5.4 Analysis of Exploratory Endpoints.

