APPENDIX C**Baseline Visit (Day 1)****VISUAL ANALOG SCALE: PATIENT DYSPNEA**

VISIT 1 (Day 1) and Date: / / / / / / / / /

[figure not shown]
To be completed by patient. "Please draw a horizontal line on the scale to show how you think your breathing is right now. The number "0" equals the worst your breathing has ever felt and the number "10" equals the best you have ever felt."

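### The top-ranked secondary endpoint, 48-hour change in dyspnea VAS, is tested without adjustment for baseline VAS: a valid test that gives up precision

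*Combined protocol and SAP*

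**What the plan says.** Section 7.2.1 lists the endpoint as "Change in the patient reported visual analog scale for dyspnea from baseline to 48 hours". Section 8.3.1 ranks it first: "The highest priority secondary endpoint will be based on the patient reported VAS dyspnea score with comparison of the change in this scale". The analysis is in section 8.5.3.1: "Changes in the VAS dyspnea scale will be analyzed via point estimates and corresponding standard deviations", followed by "Supportive between-treatment group comparisons will be conducted via the Wilcoxon rank-sum test". No covariate is named there or elsewhere for this endpoint. Section 8.5.3 applies a two-sided 5% level to all secondary endpoints.

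The baseline rating is available. Section 6.2.2 requires, for all subjects at randomization, "Assessment of the degree of congestion and dyspnea present". Appendix A schedules the same item at baseline, and Appendix C gives the 0 (worst) to 10 (best) form: "Please draw a horizontal line on the scale to show how you think your breathing is right now".

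The plan is open about low power. Section 8.3.1 states that "the current study will not have statistical power to determine if there is a difference between the tolvaptan and placebo group" on this scale. The VAS paragraph of section 2 attributes this to the variability of the measurement and adds: "The present study sample size is not adequate for this purpose". It then proposes to set the observed changes beside those of larger acute heart failure trials, as a hypothesis-generating signal.

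**The concern.** A change score subtracts the whole of the baseline rating from the 48-hour rating. If the two ratings are only moderately correlated, this over-corrects: the noise in the baseline rating is added to the outcome. On a scale bounded at 10, a patient who starts high also has little room to improve. Regression on the baseline rating lets the data decide how much of it to subtract.

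With about 20 patients per arm and randomization stratified only by site (section 5.2), the arms can differ in baseline VAS by chance, and that difference carries through to the unadjusted comparison. At stake is the precision of the endpoint that the plan ranks first among its secondary endpoints and from which it hopes to read a signal. Section 8.5.3.1 also specifies no confidence interval for the between-arm difference, which such a signal needs.

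**Working it through.** **The plan's own figure.** The only stated power is 79% for a 1 kg difference in weight change with 40 patients (section 9.2). No SD is stated there. With the pilot SD of 1.1 kg for all patients (Table 1) and 20 per arm, a noncentral t calculation gives 80.0%, or 78.1% after allowing for the Wilcoxon relative efficiency of 0.955. The figure is reproduced, but it concerns weight. No SD, correlation, effect or power is given for the VAS, so everything below rests on assumed values.

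**Variance.** Let σ be the SD at each visit (taken as equal), ρ the correlation between baseline and 48 hours, and n = 20 per arm (section 9.1).

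- Change score: (2/n) × 2σ²(1 − ρ)
- Baseline-adjusted: (2/n) × σ²(1 − ρ²) × [1 + 1/(N − 4)]. The bracket is the average cost of chance imbalance; at N = 40 it is 37/36.
- Ratio, adjusted to change: (1 + ρ)/2 × 37/36

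| ρ | (1+ρ)/2 | ratio at N = 40 | patients a change-score analysis needs to match 40 (40 ÷ ratio) |
|---|---|---|---|
| 0.3 | 0.65 | 0.67 | 60 |
| 0.5 | 0.75 | 0.77 | 52 |
| 0.7 | 0.85 | 0.87 | 46 |
| 0.9 | 0.95 | 0.98 | 41 |
| 0.95 | 0.975 | 1.00 | 40 |

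The direction does not depend on equal SDs. With SDs σ₀ and σ₁ at the two visits, the per-patient variance of change minus the residual variance after adjustment is (σ₀ − ρσ₁)², which is never negative. Only the 37/36 factor works the other way.

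**Power on the bounded scale.** Assumptions: 0 to 10 with clipping, SD 2.5, baseline mean 4, control mean at 48 hours 5.5, 20 per arm, 20,000 simulated trials per setting (Monte Carlo standard error at most 0.35 point). Entries are percentages.

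| effect | ρ | planned rank-sum on change | ANCOVA | rank ANCOVA |
|---|---|---|---|---|
| 1 point | 0.3 | 16.8 | 24.6 | 23.6 |
| 1 point | 0.5 | 22.1 | 28.7 | 27.8 |
| 1 point | 0.7 | 32.5 | 38.9 | 36.5 |
| 2 points | 0.3 | 50.2 | 70.8 | 69.1 |
| 2 points | 0.5 | 63.3 | 78.2 | 76.1 |
| 2 points | 0.7 | 83.3 | 91.1 | 89.3 |

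The ANCOVA gain is 6 to 8 points for a 1-point effect and 8 to 21 for a 2-point effect. Smaller runs under the same assumptions scatter a little more widely, so I quote 4 to 8 and 8 to 23. With no true effect, all three tests reject in 4.8% to 5.2% of trials (ρ 0.3 to 0.9).

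**Power without bounds.** With normal data and a difference of 0.5 visit-SD (4,000 trials per setting), the planned test, ANCOVA and rank ANCOVA give 25%, 36% and 35% at ρ = 0.3; 32%, 42% and 40% at 0.5; 48%, 56% and 52% at 0.7; and 92%, 94% and 87% at 0.9. In the last case rank ANCOVA falls below the planned test.

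**Chance imbalance.** The baseline difference between arms has SD σ√(2/20) = 0.316σ, or 0.79 points at σ = 2.5. Given a baseline difference D, the expected change-score difference moves by (1 − ρ)D. At ρ = 0.5 and D = 0.79 that is about 0.40 points. Over repeated randomizations it averages to zero.

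**The case against.** The strongest reply is that the plan never leans on this test. It labels the comparison supportive and the endpoint hypothesis-generating, and its main output is arm-level change with SD, which is what the cross-trial comparison in section 2 needs. A rank test is a reasonable choice for a bounded scale in small arms. That stands as a reason to keep the change summaries and to treat the matter as modest. It is not a reason to leave baseline VAS unused: a signal-seeking endpoint is best served by the tightest available estimate with an interval, and rank ANCOVA meets the wish for a rank method.

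The reply is also right that the gain depends on unknowns. A low correlation and a large effect make it look big; a correlation of 0.9 or more makes it negligible.

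Three stronger readings are tempting, and the documents do not support them.

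- A reader might infer that the planned comparison is biased or inflates the type I error. It does neither: treatment is randomized and the simulated error is about 5%.
- A reader might infer that adjustment would rescue the endpoint. For a 1-point effect, ANCOVA power is still only about 25% to 39% over ρ 0.3 to 0.7.
- A reader might extend the argument to loop-dose change (section 8.5.3.2) by adjusting for the dose at the start of Visit 2. That dose is recorded 48 hours after randomization, and section 5.5.1 allows diuretic and study drug to be changed before then in response to the patient's course. Conditioning on it could bias the comparison. Any covariate there would have to be the pre-randomization dose.

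**Conclusion.** The point holds as one of efficiency. The planned rank-sum test on change is valid but less precise than a baseline-adjusted comparison unless the two ratings are correlated at about 0.95 or more. The variance saving is about 33%, 23%, 13% and 2% at correlations of 0.3, 0.5, 0.7 and 0.9, assuming equal visit SDs and 40 patients with both ratings. The power gains further assume an SD of 2.5 and means of 4 and 5.5. That adjustment does not lose precision below that correlation is a general result; how much it gains cannot be read from the documents. The plan's own statement that the study is underpowered for this scale remains true for modest effects after adjustment, and the primary endpoint is not affected.

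**What to change.** In section 8.5.3.1, keep the mean change and SD by arm, and state that they serve the cross-trial comparison described in section 2. Replace the supportive rank-sum test with an ANCOVA of Visit 2 dyspnea VAS on treatment and baseline VAS, reporting the adjusted difference with its 95% confidence interval. If a nonparametric test is preferred, use rank ANCOVA (Visit 2 ranks on baseline ranks), and note that it loses its advantage when the correlation is very high. Leave section 8.5.3.2 out of this change.

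The cost is a sentence or two in the plan and one residual degree of freedom (38 to 37). No new data are needed. Because section 8.1.2 rules out imputation, both analyses use the same patients with two ratings. Section 2 reports that earlier changes to the analysis plan were made before unblinding, and this one should be too. If unblinding has already taken place, report the adjusted analysis as a labelled sensitivity analysis beside the planned test.

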10.1 Summary of the Risks and Benefits

General Safety Considerations. This study targets patients with worsening outpatient heart failure. The study will evaluate the addition of tolvaptan to augmentation of oral furosemide versus augmentation of oral furosemide alone in patients with worsening outpatient heart failure. Augmentation of oral loop diuretic is considered standard therapy in this target patient population. A number of moderate and large scale clinical trials have demonstrated evidence of the safety of tolvaptan in the treatment of patients for hyponatremia and patients with heart failure with and without hyponatremia. Side effects have been noted, most commonly thirst and polyuria and these may lead to discontinuation. However reduction in renal function and blood pressure or elevation of potassium are not associated with drug use; a major finding since most evidence based therapy for heart failure can produce significant renal dysfunction, unwanted hypotension and elevation of potassium that can have serious consequences.

Safety in Heart Failure. Oral tolvaptan was previously studied in the acute heart failure population in the EVEREST study, in which acute and chronic tolvaptan administration was not associated with any evidence of harm over a median follow-up of 10 months (compared to 8 days in the current study). The EVEREST study provides extensive experience with the safety of tolvaptan in heart failure. In this trial, 4133 patients with acute decompensated heart failure were randomized to either placebo or tolvaptan. The overall

rate of in hospital serious adverse events with the combination of oral Tolvaptan and IV loop diuretics was approximately 5%, and was similar between Tolvaptan and placebo. Therefore it is not anticipated that study participation will be associated with increased risks beyond that of standard therapy for decompensated heart failure.

Recurrent volume overload, driven by sodium and water retention, remains a major clinical problem in heart failure despite the use of potent diuretics acting at multiple points within the nephron. All too often patients fail to be congestion free despite the potential potency of loop diuretics in particular. Therefore potential benefits to study participants include the possibility of improvements in clinical congestion and associated symptoms (if Tolvaptan proves to be efficacious).

Risk of Overcorrection of Serum Sodium. Although the target patient population of this study is decompensated heart failure rather than hyponatremia, it must be acknowledged that there is the real potential for overlap of these two conditions in a given patient. This possibility means that there is one risk that is unique to tolvaptan versus other medications for heart failure that must be addressed: overcorrection of serum sodium. Overcorrection of serum sodium is related to the primary mechanism of action of tolvaptan which leads to greater water excretion by the kidney and consequently an increase in serum sodium. In the great majority of patients with heart failure, the increase in serum sodium following administration of tolvaptan is appropriate. However, rarely patients may experience an overcorrection of serum sodium. Overcorrection has been most commonly defined as an increase in serum sodium from baseline of > 12 mEq/Liter in a 24 hour period after tolvaptan administration.

The risk of overcorrection of serum sodium is strongly associated with the degree of reduction in serum sodium present prior to therapy. Overcorrection is generally only a potential issue when patients with hyponatremia are treated with tolvaptan. The widely accepted definition of hyponatremia is presence of a reduction in serum sodium to < 135 mEq/L. Hyponatremia can be further characterized as mild (serum sodium from 130 to 134 mEq/L) or marked (serum sodium < 130 mEq/L). A serum sodium of less than 125 mEq/L has also been defined as sufficiently reduced to warrant tolvaptan therapy as treatment regardless of the presence or absence of symptoms. Although it remains uncommon, overcorrection of serum sodium is most likely to occur in cases where serum sodium is < 125 mEq/L.

Since hyponatremia is uncommon in acute or chronic heart failure, overcorrection of serum sodium has not been reported as an issue in these studies. Review of the experience in

the EVEREST trial helps provide a clinical context concerning the potential risk of overcorrection of serum sodium specifically in patients with heart failure. Despite studying a targeted patient population of acute decompensated heart failure, hyponatremia was uncommon in the patients enrolled in this trial. A total of 4133 patients were studied, randomized to tolvaptan and randomized to placebo with an initial dose of 30 mg of tolvaptan daily. The incidence of hyponatremia at baseline was 11.5% overall (475 patients) and as expected, was similar in groups receiving tolvaptan and placebo.

Experience in the SALT trials, which used the definition above for hyponatremia (serum sodium < 135 mEq/L) as an inclusion criteria and did include patients with heart failure, can help define the risk of overcorrection of serum sodium in patients with heart failure and hyponatremia. A total of 448 patients were randomized in the SALT studies with 225 patients treated with tolvaptan and 223 patients with placebo. The initial dose of tolvaptan in these trials was 15 mg daily but could be titrated to 60 mg daily depending upon therapeutic response. In these trials only 5 patients on active therapy (2.2%) experienced a rise in serum sodium of > 12 mEq/L during any 24 hour period of treatment.

Osmotic Demyelination Syndrome (ODS). Although an increase in serum sodium can be lifesaving in acute symptomatic hyponatremia, overcorrection of serum sodium may rarely result in severe neurological dysfunction referred to as ODS. This syndrome is the general term for central pontine and extrapontine myelinolysis. Clinically ODS is characterized by dysarthria, dysphagia, behavioral disturbance, and muscle weakness which may not resolve and the condition may be fatal. A number of predisposing factors for ODS following overcorrection of serum sodium have been identified: chronic alcoholism, severe liver disease, marked malnutrition and hypoxia. Review of clinical reports of ODS suggest that while the threshold for observing this syndrome may be 8 to 12 mEq/L increase of serum sodium, most cases have occurred in the setting of significantly larger increases in serum sodium, often in excess of 20 mEq/L.

While there is no question that overcorrection of serum sodium by the criteria of an increase of > 12 mEq/L of serum sodium may rarely occur with tolvaptan therapy, the frequency with which ODS occurs in association with tolvaptan therapy remains disputed. None of the 5 patients in the SALT trials who has an increase in serum sodium of > 12 mEq/L experienced ODS (nor did any other patient in the SALT trials). No cases of ODS have been reported in patients treated with tolvaptan in randomized clinical trials including approximately 2,000 patients with heart failure. The FDA Package Insert for tolvaptan indicates that cases of ODS have been reported post marketing but the exact language in

the text concludes that the anecdotal nature of these reports does not permit assignment of causal role for tolvaptan. One example of confounding that may occur in the post marketing data is concomitant therapy with hypertonic saline. Simultaneously treatment with both tolvaptan and hypertonic saline is contraindicated, would significantly increase the risk of overcorrection and will not occur in this study. It is important to note that clinical series have found that the development of ODS may be low in the setting of overcorrection.

Implications for the Present Study. Given the study sample size of 40 patients and the planned exclusion of patients with serum sodium < 125 mEq/L, approximately 3 to 4 patients could be expected to be enrolled with hyponatremia. The low rate of overcorrection observed in the SALT Trials suggests, that even in the setting of hyponatremia, the risk of a single study patients experiencing overcorrection of sodium in response to tolvaptan would be low.

Minimizing Risk of Overcorrection of Sodium. Although the risk of overcorrection of serum sodium is low in patients with heart failure, it is appropriate to take steps to reduce the risk of this potentially very serious and rarely fatal complication.

During Screening

- 1- Patients with symptomatic hyponatremia will be excluded from the study.
- 2- Patients with severe hyponatremia, defined as serum sodium < 125 mEq/L at the time of screening, will be excluded regardless of whether they are symptomatic or not.
- 3- Patients with the following predisposing factors for ODS, assessed by the study investigator judgment, will be excluded: chronic alcoholism at the time of study, severe liver disease, marked malnutrition, and risk for chronic hypoxia.

Randomization - Initial Dose of Study Drug

4. All patients will initiate study drug tolvaptan/placebo in a hospital setting.
5. Patients who are not hyponatremic at baseline will be monitored for 8 hours for adverse effects and changes in vital signs suggestive of potential volume depletion (orthostatic decline in blood pressure and increases in heart rate) and intake and output. Review of these findings will aid in identification of patients who may be more likely to have overcorrection of serum sodium due to excess aquaresis and inadequate per oral intake. Any patient without hyponatremia at baseline who is clinically suspected to have overcorrection of serum sodium will have repeat determination of serum electrolytes and renal function at 6 hours post initial dose of

tolvaptan/placebo and these labs will be reviewed prior to their discharge from the hospital setting. Any patient subsequently found to have an increase in serum sodium > 6 mEq/L will be managed as indicated in points 6 to 9 that follow.

6. Patients who are hyponatremic at baseline will all have repeat determination of serum sodium 6 hours after their initial dose of study drug. Any of these hyponatremic patients found to have a rise in serum sodium of > 6 mEq/L at the 6 hour time point will receive treatment with intravenous D5W designed to limit further increases in serum sodium. Intravenous D5W will administered at the rate of 3 mL/kg per hour (210 mL for a 70 kilogram patient) which is expected to reduce serum sodium from 1 to 2 mEq/L per hour.
7. Patients with this degree of early increase in serum sodium will have repeat serum sodium and other electrolytes plus BUN and Creatinine determined at 2 hour intervals of D5W administration. Administration of D5W will stop when the patient is at least 14 hours post their initial dose of study drug and the serum sodium is < 8 mEq/L above their baseline values.
8. Patients with this degree of early increase in serum sodium will be observed for a minimum of 24 hours after their initial dose of study medication. They will also have repeat determination of serum sodium and other electrolytes plus BUN and Creatinine 20 hours after their initial dose of study medication and these values will be reviewed prior to their discharge from the hospital setting. If their serum sodium remains < 12 mEq/L above baseline at the 20 hour blood draw and they are clinical stable they will be discharged from the hospital setting at the 24 hour point. Any patient that is found to have a 20 hour serum sodium that is > 12 mEq/L from their baseline will receive additional D5W as above with repeat determinations of serum sodium until their value is < 12 mEq/L above their baseline. At that time if they are clinically stable then they will be discharged from the hospital setting.
9. Once discharged hyponatremia patients with overcorrection of sodium will be followed in the study but not treated further with study medication. They will return for a study visit Day 3 where they will have repeat determination of serum electrolytes, including serum sodium, as well as BUN and Creatinine. In the unlikely event that they are found to have serum sodium > 18 mEq/L above their baseline value at this visit, they will be considered for per oral hydration or administration of additional intravenous D5W at the discretion of the clinical investigator.

10. Any patient found to have overcorrection (a rise in serum sodium of > 6 mEq/L at the 6 hour time point) will still continue to be followed in the study and treated with augmented loop diuretic and other medical approaches as needed. They will be seen at Day 8 for evaluation as planned for the protocol and continue to have 30 day follow-up as well as additional clinic visits at any point during the study.
11. Patients found to be hyponatremic will also be monitored for development of symptoms during the study related to reduced serum sodium. As a precaution, patients with symptomatic hyponatremia are excluded from the study. Patients with heart failure who present with hyponatremia are very commonly asymptomatic and the condition is chronic and does require therapy to reverse the hyponatremia per se. Patients with heart failure and chronic hyponatremia rarely become symptomatic. Patients enrolled in the study with asymptomatic hyponatremia will be cautioned to monitor for changes in mental status, nausea, and lethargy between their baseline visit and follow-up visits. Patients will be instructed to contact the study investigators should these symptoms develop and they will be seen for follow-up evaluation as needed.

Hepatic Toxicity. The FDA proposed label changed for tolvaptan in 2013. These changes concerning tolvaptan use indicated that the drug should not be used for longer than 30 days and should not be used in patients with underlying liver disease. These changes were made after 3 cases of suspected liver injury with Tolvaptan were identified in the TEMPO study. TEMPO studied a significantly higher tolvaptan dose (60 mg per day and titrated up to 120 mg per day) and a longer duration of treatment (36 months) than in the planned study (30 mg for 8 doses – with 8 days of exposure). The patient population in TEMPO (Autosomal Dominant Polycystic Kidney Disease) is different than the one proposed for this study. The liver abnormalities occurred after at least 3 months of treatment and all 3 patients improved following discontinuation of treatment. The study protocol for this trial will exclude patients with known underlying liver disease to be consistent with the revised FDA labeling.

